1.6. RANDOMIZATION

A randomized allocation to study and control groups using computer-generated random numbers was done by the trial statistician.

Equal numbers were randomly allocated to the two groups for the two hospitals.

Based on the sample size the plan was for the statistician to prepare random numbers for 1,162 patients. Half of these numbers were labelled with A which represented the intervention 10mg/kg TXA and oxytocin 5IU e.g. random number 4A, represented random number 4, allocated to group A. The other half had the extension B (control group) to receive Oxytocin 5IU only.

The computer-generated numbers assigned the trial group and also a unique participant number. The numbered folded slips of paper were placed into sealed identical envelopes by the principal investigator. The sealed envelopes were kept in a box at each hospital in a locked-up room. At the beginning of the trial, TXA for 200 patients was available. The statistician therefore initially prepared random numbers for 400 patients (200 with the extension A and 200 with the extension B), half of which were prepared for HMH (1 – 200) and the other half for MNMH (1 – 200). A further 106 were prepared when the 400 numbers were used up to make the total number recruited 506 during the initial trial period.

The patients were enrolled by the principal investigator or the research assistants on the day before their scheduled caesarean section. Once they met the study criteria per the screening tool (see **Error!**

Reference source not found.), informed consent was obtained (**Error! Reference source not found.** & **Error! Reference source not found.**). The participant was asked to pick an envelope from the box. The envelope would then be opened by either the participant or the researcher.

The study number would then be entered on the data collection tool as the study serial number. A unique study sticker labelled 'Group A' / 'TXA' or 'Control' would be attached to the patient's notes. The data tool would then be inserted into the notes together with a prescription form if in group A for the attention of the theatre staff and anaesthetists. (Refer to **Error! Reference source not found.**). Only the data tool was attached to the control group patient's notes. (**Error! Reference source not found.**). A list matching the serial number to the allocated group was compiled to match the original randomization.

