1.7. BLINDING

There was no blinding after the sealed envelopes had been opened. After randomization, the participants and trial staff were aware of the trial group to which the patient had been allocated.

A completely blinded trial would have required fully dedicated staff. Such a trial would have put pressure on already busy anaesthetists. However, there was an agreement from the departments that the TXA would be given according to the study protocol.

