1.10. ASSESSMENT

Data were collected and recorded on the data collection tool. Any adverse event was to be reported on the MCAZ/MRCZ adverse event reporting form.

Vital signs (heart rate, blood pressure, respiratory rate) were recorded before surgery, immediately after placental delivery, and 1 to 2 hours after birth.

Full blood count (FBC), urea & electrolytes (U&E) and liver function tests (LFTs) were performed a day before delivery and on the second day after delivery.

Estimated blood loss (EBL) was determined using the difference in haematocrit values taken before and 48 hours after caesarean delivery according to the formula:

$$= \text{EBV} \times (\text{Preoperative haematocrit} - \text{Postoperative haematocrit})$$

Preoperative haematocrit

Where EBV (estimated blood volume) in ml is equal to the woman's weight in kg \times 85 ⁽³⁸⁾.

As haematocrit values were not consistently available, EBL was also determined using the haemoglobin (Hb) value using the Meunier's formula $BV \times [(Hb_i - Hb_e)/(Hb_e)]$, where BV is blood volume, Hb_i is initial Hb, and Hb_e is end Hb⁽⁵²⁾.

Standard EBL based on visual estimates made by anaesthetist after assessment of patient's linen and abdominal swabs was also recorded.

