1.11. STATISTICAL METHODS

Data analysis was conducted using Stata v15 (Stata Statistical Software: Release 15. College Station, TX: StataCorp LLC) following the CONSORT guidelines for reporting RCTs⁽⁵⁵⁾.

The primary analysis compared women given a low dose of TXA (10mg/kg) administered 10 minutes before elective caesarean section with prophylactic oxytocin administration to those given prophylactic oxytocin alone.

Baseline characteristics were compared between the groups to check the adequacy of randomization. Differences between patients lost to follow-up and included patients were also assessed. The intention-to-treat analysis was followed. This is a statistical concept whereby every participant in the study is accounted for in the analysis according to the randomization treatment assignment regardless of whether there is noncompliance, protocol deviations, withdrawal from the study, and anything happens after randomization⁽⁵⁶⁾.

Categorical data were reported using frequencies and proportions while continuous data were summarized using means and standard deviations for normally distributed data, and medians and quartile range where data was not normally distributed. Comparisons for categorical data were done using the chi-square test or Fisher's exact test when the sample size was small.

For continuous data, the t-test was used to compare differences between the groups and the analysis of variance (ANOVA) was used for comparing more than two groups. Where data were not normally distributed, the nonparametric Kruskal Wallis test was used to compare differences in continuous outcome for more than two groups. The Mann-Whitney U test was used to compare two groups where data were not normally distributed. Effect estimates were presented with relative risk measures and associated 95% confidence intervals. Any subgroup analysis was conducted as the primary analysis.

An analysis was conducted after 506 participants had been recruited to check if there are any significant differences in adverse events in the two groups.

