1.14.2. Secondary Outcomes

1. Incidence of PPH defined by blood loss equal to or exceeding 1000 ml following elective caesarean section

- Based on visual estimation

2. Estimated blood loss during caesarean section

- Based on visual estimate of blood loss and calculated estimates

3. Need for blood transfusion

- Mean or median number of units of red blood cells transfused up to day 2 postpartum

4. Use of additional uterotonicics (such as oxytocin infusion or prostaglandins)

- Number of participants who required additional uterotronics

5. Incidence of emergency surgical interventions for PPH up to day 2 post-surgery

6. Mean change in HCT up to day 2 post-surgery

- Difference between the HCT on the day before surgery and day 2 post-surgery

7. Mean peripartum change in haemoglobin up to day 2 post-surgery

- Difference between the haemoglobin on the day before surgery and at day 2 post-delivery

8. Duration of mother's hospital stay

9. TXA side effects

- number of participants with headache, anaphylaxis, nausea, diarrhoea, dizziness, fatigue, nasal sinus complaints, transient visual disturbances, abdominal pain, complaints of feeling faint, reported by anaesthetists and theatre staff [time frame: up to discharge from the recovery ward on day of surgery]
- number of participants with deep venous thrombosis, pulmonary embolism, myocardial infarction, or any thrombotic event confirmed by laboratory investigations up to day 2 post-surgery
- number of participants with seizures up to day 2 post-surgery
- number of participants with renal failure (defined by the need for dialysis) up to day 2 post-surgery
- number of participants with hypotension reported by anaesthetists and theatre staff [time frame: up to discharge from the recovery ward on day of surgery]
- Vital signs before surgery
 - Heart rate before surgery
 - Systolic BP before surgery
 - Diastolic BP before surgery

- Vital signs after placental delivery
 - Heart rate after delivery of the placenta
 - Systolic BP after delivery of the placenta
 - Diastolic BP after delivery of the placenta
- Post-caesarean delivery creatinine (mg/dL)
- Postoperative urea g/L
- Postoperative aspartate transaminase (IU/L)
- Postoperative alanine transaminase (IU/L)
- Postoperative total bilirubin (IU/L)

10. Neonatal outcomes

- Birth weight in grams determined on the date of delivery
- Apgar scores at 1 and 5 minutes on the date of delivery

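### Hypotension is counted from the reports of staff who know the arm, with no blood-pressure criterion, so a between-arm difference may reflect reporting rather than TXA, in either direction; a thresholded count from the scheduled readings should stand beside it.

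*Combined protocol and SAP*

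**What the plan says.** Section 1.14.2, item 9 (TXA side effects), includes the "number of participants with hypotension reported by anaesthetists and theatre staff", counted until the woman leaves recovery on the day of surgery. Neither this line nor any other part of the supplied text gives a systolic value, a diastolic value or a size of fall that makes a case. Another line in the same item does carry a criterion: "number of participants with renal failure (defined by the need for dialysis) up to day 2 post-surgery".

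Section 1.7 states: "After randomization, the participants and trial staff were aware of the trial group to which the patient had been allocated". Section 1.6 puts a group sticker on the notes and, for TXA women, adds a prescription form "for the attention of the theatre staff and anaesthetists". Section 1.8 has the anaesthetist prepare the TXA.

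Section 1.10 says: "Vital signs (heart rate, blood pressure, respiratory rate) were recorded before surgery, immediately after placental delivery, and 1 to 2 hours after birth". Item 9 takes up part of this. It lists heart rate, systolic and diastolic pressure before surgery and again after placental delivery, for example "Systolic BP after delivery of the placenta". It does not list the 1 to 2 hour reading.

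On analysis, section 1.11 says: "Comparisons for categorical data were done using the chi-square test or Fisher's exact test when the sample size was small". It also says: "An analysis was conducted after 506 participants had been recruited to check if there are any significant differences in adverse events".

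**The concern.** With no criterion, each member of staff decides whether a fall in pressure is worth reporting. That decision is made knowing whether the woman received TXA, for an outcome filed under TXA side effects. Staff may look harder after giving the drug, or may be slower to report if they favour it. Either way, the count combines how often hypotension occurred with how often it was reported.

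The second objective of the trial (section 2.4) is to determine the potential adverse effects of TXA. Differential reporting is not removed by recruiting more women or by analysing by intention to treat. A larger sample makes a spurious difference more likely to reach significance. The other staff-reported symptoms in item 9 share the weakness, but the plan schedules no objective measurement for them. For hypotension it does, so an improvement is available at little cost.

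**Working it through.** **Inputs from the documents.** The planned size is 581 per group (section 1.4). The adverse-event analysis was done at 506 women (section 1.11), which is 506 / 2 = 253 per arm if the split is equal. The test is chi-square at the two-sided 5% level (sections 1.4 and 1.11).

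**The plan's own figure.** The documents give no figure for hypotension. The per-arm size used below does reproduce. With 2.1% v 5.8%, 90% power and unrounded normal quantiles, the section 1.4 formula gives 580.3, which rounds up to 581. No stated figure is in dispute.

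**Assumed inputs.** The true hypotension rate p is equal in both arms, at 10%, 20% or 30%. The share of episodes reported is s_T = 0.90 under TXA, and s_C = 0.85, 0.80 or 0.70 under control. The documents give none of these values.

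**Formulas.** The reported rates are a = p × s_T and b = p × s_C, so the expected relative risk is a / b = s_T / s_C whatever the value of p:

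- 0.90 / 0.85 = 1.06
- 0.90 / 0.80 = 1.125, shown as 1.13
- 0.90 / 0.70 = 1.29

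With m = (a + b) / 2, SE0 = √[2m(1 − m)/n] and SE1 = √[(a(1 − a) + b(1 − b))/n], the chance of p < 0.05 is

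Φ[(|a − b| − 1.96·SE0)/SE1] + Φ[(−|a − b| − 1.96·SE0)/SE1].

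**One case in full** (p = 20%, 0.90 v 0.70, n = 581):

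- a = 0.18, b = 0.14, m = 0.16
- SE0 = √(2 × 0.16 × 0.84 / 581) = 0.02151, and 1.96 × SE0 = 0.04216
- SE1 = √[(0.18 × 0.82 + 0.14 × 0.86)/581] = 0.02148
- first term Φ[(0.04 − 0.04216)/0.02148] = Φ(−0.10) = 0.46; the second term is negligible

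The chance of a falsely significant result is therefore about 46%.

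**All cases** (chance of p < 0.05 with no true difference):

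| Reported, TXA v control | Relative risk | 253 per arm: p = 10%, 20%, 30% | 581 per arm: p = 10%, 20%, 30% |
|---|---|---|---|
| 90% v 90% | 1.00 | 5%, 5%, 5% | 5%, 5%, 5% |
| 90% v 85% | 1.06 | 5%, 6%, 7% | 6%, 7%, 9% |
| 90% v 80% | 1.13 | 7%, 9%, 12% | 9%, 15%, 22% |
| 90% v 70% | 1.29 | 13%, 23%, 35% | 24%, 46%, 67% |

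Exact enumeration of the two binomials gives the same values after rounding. If the shares are swapped between the arms, the chances are unchanged and the relative risks invert to 0.94, 0.89 and 0.78. The same mechanism could therefore make TXA look protective or hide a real excess.

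**Timing of the measured readings.** Section 1.8 gives TXA before skin incision and oxytocin at delivery of the baby. Under section 1.10, the first reading that certainly follows TXA is taken just after placental delivery, so it comes after incision, delivery and oxytocin. Section 1.10 does not say whether the reading before surgery precedes or follows the TXA. The scheduled readings therefore do not cover the infusion period, and the staff report is the only measure in the plan that does.

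**The case against.** The strongest reply is that a measured comparison is already planned. Item 9 lists systolic and diastolic pressure at two time points, and section 1.11 supplies tests for continuous data. This stands in part. A reader might infer that the staff report is the only information on blood pressure, or that the plan considered measured pressure and set it aside. The documents support neither: the readings are listed, and no reason for leaving them out of the hypotension count is given. But comparing average pressures does not define or repair a count of affected women, and the 1 to 2 hour reading is not among the outcomes.

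A second reply is that scheduled readings are a poor substitute, because they miss brief falls during the infusion and also reflect oxytocin and blood loss. This stands. A reader might conclude that a measured count should become the main comparison and the staff count be reduced to description. That would demote the only measure covering the infusion and could lean towards finding no harm.

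Third, both the size and the direction of the bias are assumed. This also stands. With a 5-point reporting gap, the error rate stays near nominal (5–9%).

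Three smaller points are fair. Section 1.10 does not promise complete readings or say who takes them. The data collection tool is not in the supplied text and might hold a definition. The open-label design is disclosed, with practical reasons, in section 1.7.

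**Conclusion.** The point holds as a weakness in how one secondary safety outcome is defined. The hypotension count has no criterion and comes from staff who know the arm, so a between-arm difference in it cannot by itself be attributed to TXA. Under the assumed inputs, the chance of a falsely significant difference runs from about nominal to 35% at 253 per arm and to 67% at 581 per arm. It depends mainly on how unequal reporting is, which the documents cannot tell us.

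A reader might infer that reporting was in fact biased, or that it was biased against TXA. The documents show that the opportunity existed, not that bias occurred or in which direction. The primary outcome is unaffected. Hypotension could feed the adverse-event comparison at 506 women, although the documents do not say which events that comparison covered.

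**What to change.** Add to item 9 a count of women who meet one numerical hypotension criterion. The investigators should choose it without reference to by-arm results. This needs particular care because adverse events in the first 506 women have already been compared by group. Apply the criterion identically in both arms to the readings taken after placental delivery and at 1 to 2 hours. Report the number of missing readings by arm.

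Present this count beside the staff-reported count, with equal standing. Label the staff count as reported by unblinded staff, and do not attribute a difference seen only there to TXA without that caveat. If the data collection tool already holds a definition, state it in item 9.

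The cost is one line in the outcome list, one derived variable from readings the plan already schedules, and one row in the safety table. It needs no blinding and no new measurement. The downside is that the scheduled readings miss brief falls during the infusion and also reflect oxytocin and blood loss, so neither count replaces the other.

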Uterine atony is the most common cause of PPH ⁽¹³⁾. Uterotonics already address this as they have an effect on the myometrium. Their contractile effects close off the large spiral arteries pouring with blood from the placental bed. 40 – 70% of women with marked clotting disorders will not have PPH as the main mechanism for achieving haemostasis after childbirth is myometrial contraction compressing the uterine vessels rather than clotting. Clotting is the primary mechanism that would be useful where women have the deadly form of ongoing or delayed PPH. In this subgroup of women, bleeding is from spontaneous or iatrogenic lacerations to the genital tract, or trauma and they tend to bleed vaginally or into the abdomen. With its antifibrinolytic activity, TXA potentiates clotting thereby preventing PPH in this subset. This is the group of women who tend to collapse 1 – 3 hours after delivery from the deadly ooze. This subgroup of women is the group in which TXA was found to have the maximum effect in the WOMAN Trial ⁽¹³⁾. It follows, therefore, that women with iatrogenic trauma at caesarean section are also likely to benefit from this intervention.

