1.8. INTERVENTION

The participants in the intervention arm received TXA (10mg/kg) administered slowly over 5 minutes intravenously (iv) 10 minutes prior to skin incision and prophylactic oxytocin (5 IU iv) slow administration by the anaesthetists on delivery of the baby. Participants in the control group received prophylactic oxytocin (5 IU iv) only on delivery of the baby. 5IU of Oxytocin were administered slowly intravenously as recommended by the WHO in 2012 ⁽¹²⁾. Updated recommendations were then published by WHO in 2018

after ethical approvals had been obtained and came to the attention of the principal investigator after the initial planned period of data collection (1 January 2018 to 31 December 2018) recommending the use of 10IU of oxytocin in the third stage. No change was made to the protocol during the data collection period⁽³⁾. All patients continued to receive 5IU of prophylactic oxytocin.

TXA (10mg/kg) solution for injection from the vial was diluted with 100 – 200ml electrolyte solution such as Normal Saline, Ringers Lactate solution, dextrose/water for injection on the same day it was to be used by the anaesthetist at the dose prescribed. Intravenous administration at a rate of 100mg or fraction thereof over at least 1 minute – usually at least 5 minutes for each patient was done. The administration was to be done at least 10 minutes before skin incision^(32, 33, 37, 38).

No additional prophylactic uterotronics were to be administered to the patient based on the anaesthetist's or surgeon's subjective preferences. Several local surgeons routinely add misoprostol for select cases at caesarean section. A recent local unpublished study conducted in 2017 concluded that adding misoprostol to the routine prophylactic oxytocin did not reduce the occurrence of PPH in patients undergoing low risk elective caesarean section⁽⁵¹⁾. Therefore, additional uterotronics were to be administered only if clinically indicated.

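### Vital signs recorded 1–2 hours after birth appear in no outcome or analysis, while pre-surgery vital signs of unstated timing are listed as a TXA side-effect outcome

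*Combined protocol and SAP*

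**What the plan says.** Section 1.10 (Assessment) sets the measurement schedule: "Vital signs (heart rate, blood pressure, respiratory rate) were recorded before surgery, immediately after placental delivery, and 1 to 2 hours after birth".

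Section 1.14.2 (Secondary Outcomes) has an item headed "9. TXA side effects". Its vital-sign entries are "Vital signs before surgery" and "Vital signs after placental delivery", each covering heart rate, systolic pressure and diastolic pressure. There is no entry for 1–2 hours after birth.

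Section 2.2.4, on women whose bleeding is ongoing or delayed, says: "This is the group of women who tend to collapse 1 – 3 hours after delivery from the deadly ooze". It adds: "This subgroup of women is the group in which TXA was found to have the maximum effect in the WOMAN Trial".

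Section 1.8 gives the timing of the drug: "The administration was to be done at least 10 minutes before skin incision". Neither section 1.10 nor section 1.14.2 places the pre-surgery reading before or after that infusion.

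Section 1.11 (Statistical Methods) provides a t-test or a Mann-Whitney test for two-group comparisons of continuous data. It mentions no covariate adjustment and does not name the vital signs. It plans a separate baseline comparison without listing the variables, and it describes an analysis, aimed at adverse events, after 506 participants.

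**The concern.** The measurement schedule and the outcome list do not match, in two ways.

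First, a reading taken before the drug cannot be a side effect of it. If the pre-surgery values were taken before TXA, three of the six listed vital-sign comparisons test only the randomization, and they belong in the baseline comparison that section 1.11 already plans. If they were taken after TXA and before incision, they could show an early haemodynamic effect, but a reader would need to be told so. As written, the result cannot be interpreted either way.

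Second, the 1–2 hour reading has no stated use, although the document's own rationale points to the hours after delivery. At stake are some safety information and some precision on a secondary outcome, both obtainable from data that section 1.10 says were recorded.

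**Working it through.** **Recorded against listed**

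| Reading | Recorded (1.10) | Listed as outcome (1.14.2, item 9) |
|---|---|---|
| Before surgery | yes | heart rate, systolic, diastolic |
| Immediately after placental delivery | yes | heart rate, systolic, diastolic |
| 1–2 hours after birth | yes | none |

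Three measures at three times give 3 × 3 = 9 recorded values per woman. Six are listed and three are not. Respiratory rate is also recorded, and it is listed at no time point.

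**Against the document's own window.** Section 2.2.4 puts collapse from delayed bleeding at 1–3 hours after delivery. The 1–2 hour reading lies wholly inside that window, though it does not reach the 2–3 hour part. The only post-delivery reading that is listed, immediately after the placenta, comes before the window opens.

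**Timing of the pre-surgery reading.** TXA is given at least 10 minutes before incision, so a reading described only as before surgery could fall on either side of it:

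- before TXA: a baseline value, suitable as a covariate and not as an outcome;
- after TXA: a possible early outcome, and unsuitable as a covariate because the treatment may have changed it.

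**What adjustment would gain.** The plan gives no figure here. Let r be the correlation between the baseline and follow-up values. Then the variance of the adjusted difference divided by that of the unadjusted difference is 1 − r². The documents do not give r, so it is an assumption shown over a range:

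| Assumed r | 1 − r² | Variance reduction |
|---|---|---|
| 0.2 | 0.96 | 4% |
| 0.4 | 0.84 | 16% |
| 0.6 | 0.64 | 36% |

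On an absolute scale, assume a systolic SD of 15 mmHg and take the planned 581 per group. The unadjusted SE is 15 × √(2/581) = 0.88 mmHg. At r = 0.6 it becomes 0.88 × √0.64 = 0.70 mmHg.

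**How large a signal to expect in the means.** Section 1.4 assumes PPH rates of 5.8% and 2.1%, a difference of 0.037. If every PPH case had a heart rate 20 beats per minute higher at 1–2 hours (an assumption), the group means would differ by 0.037 × 20 = 0.74 beats per minute.

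**Sample size.** The 581 per group in section 1.4 is reproduced by the stated formula with unrounded normal quantiles. It rests on the PPH rates alone, so nothing here changes it.

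**The case against.** The best defence is that the trial already measures delayed bleeding by stronger means. The primary outcome is blood loss calculated from values before and 48 hours after delivery, which takes in a slow ooze. Transfusion, emergency surgery for PPH, and the changes in haematocrit and haemoglobin are followed to day 2. Reported hypotension is counted up to discharge from the recovery ward, which may overlap the 1–2 hour period. This stands. A reader might infer that the 1–2 hour reading is the measurement most relevant to delayed bleeding; the documents do not support that, and the 0.74 beats per minute above shows how far a comparison of means dilutes events in a few women. The hypotension count is still no substitute for the recorded values, because it has no stated threshold and is reported by staff who know the allocation.

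A reader might also infer that the 1–2 hour values were discarded. No sentence says so, and the general methods in section 1.11 could be applied to them. The text supports only that no outcome or analysis names them.

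Nor can it be said outright that half of the listed comparisons show nothing but chance imbalance. That follows only if the reading preceded TXA.

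Baseline adjustment is not needed for validity: the unadjusted comparison is unbiased under randomization. The gain is in precision, and it is small if r is low.

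Finally, the change is not free of drawbacks. The trial is open-label, the document is written in the past tense, an analysis at 506 participants has been done, and section 3.16 says the DSMB reviewed the analysis prepared for the report. An outcome added now is post hoc. Completeness of the 1–2 hour values is also unknown; section 1.10 concedes that haematocrit values were not always available.

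**Conclusion.** The point holds as a minor one. One of three recorded vital-sign time points, lying inside the document's own window for delayed bleeding, is named in no outcome or analysis. Another is listed as a side-effect outcome without the timing needed to interpret it. If that reading preceded TXA, three of the six listed comparisons are baseline comparisons. The value of using it as a covariate depends wholly on the assumed correlation: slight at the low end of the range, worthwhile at the high end. The 1–2 hour values would supplement the blood-loss, transfusion and hypotension outcomes, not replace them. The conclusion about omission rests on the absence of any mention, not on a statement that the values were left out.

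**What to change.** 1. In sections 1.10 and 1.14.2, state whether the pre-surgery reading was taken before or after TXA.
2. If before, move it from item 9 to the baseline table. Analyse heart rate, systolic and diastolic pressure after placental delivery and at 1–2 hours by linear regression adjusted for the matching pre-surgery value, and report the mean difference with its 95% CI. Add this model to section 1.11.
3. If after, keep it as an early outcome, say so, and do not adjust for it.
4. Date the addition, label the 1–2 hour comparisons post hoc and exploratory, and report by group how many women have a value.

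The cost is a change of wording and three extra exploratory comparisons. According to section 1.10 the readings were already recorded, so no new data collection is required.
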